### **4.3 Excluded or Vulnerable Populations**

*Sufficient fluency in English is required to complete consent, study forms, and questionnaires. During screening, a member of the research team will abstract from the medical record (if available) whether the participant is English speaking. A member of the research team will ask the participant whether they have sufficient fluency in English to complete the consent study forms and questionnaires.*

[figure not shown]
*Pregnant women will be enrolled and are considered a vulnerable population.*

## **5.0 Subject Enrollment**

*Aim 1: We will recruit 9-12 (3-4 from each group) physician attending/resident, nurse-midwife and nurse in the Center for Women's Health at UIC.*

*Aim 2: We will recruit 60 pregnant women to enroll 40 and obtain a final sample of 32 women (16/arm). Women will be referred by their provider to the study team and recruited following their initial new OB visit either in-person at an upcoming clinical visit, by phone, by text or via MyChart messaging to determine interest and confirm eligibility. Only one MyChart message will be sent to gauge individual interest. Potential participants can decline participation in the study through MyChart messaging. A member of the research staff will indicate through MyChart that the participant's response will be directed to a member of the research staff only and not to the practitioner. Women will also be identified and pre-screened by study staff through provider scheduling records and patient EMR to assess provider referral rates. We have found in our previous studies that waiting until after the new OB visit is completed streamlines the recruitment process substantially, since the initial visit yields a detailed*

*History and Physical, estimated dating of gestational age, and new OB clinical labs. Interested and eligible women will be invited to schedule a baseline research visit.*

## 6.0 Study Design and Procedures

### Aim 1.

*Center for Women’s Health providers agreeing to participate will engage in a one-on-one interview with study staff. The interview consists of prepared questions as well as organic dialogue and subsequent questions stemming from the interview responses. The interview will take place in person at UIC in a private office in the College of Nursing or College of Medicine (with COVID distancing and masking in place) or via phone or UIC hosted video conferencing platform, depending on provider preference. The one-time conversation will be audio recorded and will last approximately 30-60 minutes. The provider/participant will also complete a brief 5-minute demographics questions on a study provided tablet via REDCap. Provider/subjects will be compensated with a \$25 Starbucks gift card upon completion of the interview.*

**Study Arms.** Women will be randomly assigned (3:1) to one of the two study arms described below. Women will not be blinded to their treatment assignment. Women will receive a month's worth of supplements at a time. Refills will occur at monthly research visits that are coordinated with clinical care. Based on our current probiotic supplementation trial, women receive between 5-6 refills over the course of their pregnancy depending on the timing of their study entry. We have opted to test once daily Lf (250mg) versus a lower dose (100mg) taken twice daily (as was used by our team member [name] in her previous trial) due to the common availability of Lf formulations in the U.S. commercial market, as well as the logistics around once vs. twice daily supplementation in our patient population. The supplements will be dispensed in bottles by the UIC Investigational Drug Service.

**Once daily Oral Lf (250mg).** Women assigned to this group will be instructed to consume an oral Lf capsule one hour prior to their afternoon meal and two prenatal vitamin/mineral supplement gummies without iron with omega-3 fatty acids before bed from early second trimester (15 - 24 WG) up through delivery. Women are advised to consume the Lf prior to meals, given our team member [name]'s unpublished work shows its superior efficacy for improving iron and hematological parameters among pregnant women with hereditary thrombophilia versus when consumed with meals. The 250mg Lf capsule will be sourced from Jarrow Formulas (Los Angeles, CA. The supplement (**Fig. 2**), available commercially, has been previously tested in pregnancy and includes 250mg Lf in addition to cellulose, magnesium stearate (vegetable source), silicon dioxide, and gelatin capsule material. Jarrow sources their Lf from Glanbia Nutritionals (Chicago, Illinois). Per the manufacturer, the Lf is approximately 14.3% saturated with iron or contains 17.6 mg/100g; we will confirm this with our own purity testing as described below. The prenatal vitamin/mineral gummies will be a commercially available product (OLLY The Essential Prenatal Multi). The nutritional content of the prenatal gummies is presented in **Fig. 3**. Women in both groups will be advised to consume an iron-rich diet and provided a handout detailing foods rich in heme and non-heme iron.

Figure 2. Jarrow Formulas Oral Lactoferrin supplement Facts Label

Supplement Facts		
Serving Size 1 Capsule		
Servings Per Container 60		
Amount Per Serving	% DV	
Lactoferrin (Apolactoferrin)	250 mg	†
† Daily Value not established.		

Figure 3. OLLY The Essential Prenatal Multi, Supplement Facts

Supplement Facts			
Serving Size 2 Gummies			
Servings Per Container 30			
Amount Per Serving	% DV for Pregnant & Lactating Women	Amount Per Serving	% DV for Pregnant & Lactating Women
Calories	30	Folate	667 mcg DFE 111% (400 mcg folic acid)
Total Carbohydrate	6 g 2%†	Vitamin B12 (as cyanocobalamin)	8 mcg 286%
Total Sugars	4 g **	Choline (as choline bitartrate)	10 mg 2%
Includes 4g Added Sugars	8%†	Zinc (as zinc sulfate)	3.8 mg 29%
Protein	less than 1 g	Sodium	5 mg <1%
Vitamin A (as retinyl palmitate)	1200 mcg 92%	Omega-3s (from fish oil)	70 mg **
Vitamin C (as ascorbic acid)	30 mg 25%	DHA (docosahexaenoic acid)	50 mg **
Vitamin D (as cholecalciferol)	10 mcg (400 IU) 67%	EPA (eicosapentaenoic acid)	10 mg **
Vitamin E (as dl-alpha tocopheryl acetate)	6.8 mg 36%	Other Omega-3s	10 mg **
Niacin (as niacinamide)	20 mg 111%		
Vitamin B6 (as pyridoxine hydrochloride)	2.5 mg 125%		
†Percent Daily Values (DV) are based on a 2,000 calorie diet.			
**Daily Value (DV) not established.			

*Usual Care (Control). Women assigned to this group will be instructed to consume a commercially available prenatal vitamin/mineral supplement with iron and omega-3 fatty acids (Prenatal 1, Bayer Healthcare, Whippany, NJ) before bed from early second trimester (15-24 WG) through delivery. To minimize variability in prenatal vitamin/supplement use across the participants, we have opted to standardize the prenatal vitamin/mineral supplement by providing women in the usual care arm a supplement that is nutritionally like what is prescribed by the Center for Women’s Health providers. The nutritional content of the study-provided prenatal vitamin/mineral supplement is presented in Fig. 4. Women will be advised to consume an iron-rich diet and provided a handout describing foods rich in heme and non-heme iron.*

Figure 4. Prenatal-1, Bayer Healthcare, Supplement Facts

Supplement Facts		
Serving Size: One softgel		
	Amount Per Serving	% Daily Value for Pregnant and Lactating Women
Calories	5	
Calories From Fat	5	
Total Fat	0.5 g	*
Polyunsaturated Fat	0.5 g	*
Cholesterol	25 mg	*
Total Carbohydrate	0 g	*
Sugars	0 g	*
Vitamin A (50% as beta-carotene)	4000 IU	50%
Vitamin C	60 mg	100%
Vitamin D	400 IU	100%
Vitamin E	30 IU	100%
Thiamin (B 1 )	1.7 mg	100%
Riboflavin (B 2 )	2 mg	100%
Niacin	20 mg	100%
Vitamin B 6	2.5 mg	100%
Folic Acid	800 mcg	100%
Vitamin B 12	8 mcg	100%
Biotin	300 mcg	100%
Pantothenic Acid	10 mg	100%
Calcium	200 mg	15%
Iron	28 mg	156%
Iodine	150 mcg	100%
Magnesium	50 mg	11%
Zinc	15 mg	100%
Copper	2 mg	100%
Omega-3 Fatty Acids (from fish oil)	235 mg	*
DHA (docosahexaenoic acid)	200 mg	*
EPA (eicosapentaenoic acid)	35 mg	*

*Purity Testing of Oral Lf Capsules. Purity testing of the Lf capsules will be conducted using SDS-PAGE and silver nitrate staining, concentration via UV spectroscopy, iron saturation via spectroscopy and lipopolysaccharide contamination by Limulus Amebocyte Lysate assay (Sigma Aldrich, St. Louis, MO). Lf purchased from Sigma Aldrich will serve as the reference standard (St. Louis, MO). All purity testing will be conducted by Avomeen Analytical Services (Ann Arbor, MI).*

*Study Feasibility. We will collect detailed records of the number of women eligible and then referred by Center for Women’s Health clinical staff to the research team. We will also track the number of referred women approached (by phone & in person) by our research team for enrollment and the number of women who decline and their reasons for non-enrollment. Once a woman is enrolled in the study, attendance at study visits, completeness of data, and overall and treatment specific loss to follow-up/withdrawal will be closely monitored. To track progress of subjects through the trial, we will adhere*

to and update weekly the Consolidated Standards of Reporting Trials guidelines subject flow diagram. Women who voluntarily withdraw will be asked to provide reasons for revoking their enrollment. To further supplement these process measures, the study coordinator will take detailed notes during weekly research clinic meetings to document barriers to and facilitators of subject enrollment and retainment in the study, which will be used in our implementation analysis. Rates of enrollment and retainment are key feasibility outcomes. To facilitate recruitment and retention, transportation and participation monetary incentives will be provided. Together these activities will allow for the assessment of success and failure points to guide future work. **Expected results:** The study will be deemed feasible if clinicians refer  $\geq 75\%$  of women that are eligible, we recruit  $\geq 50\%$  of those referred at a minimum rate of 3-4 women/month, women complete  $\geq 80\%$  of planned study visits, and we retain  $\geq 80\%$  of women in both treatment arms through delivery.

**Optimizing Adherence.** Hand pill counts will be performed by UIC Investigational Drug Service. **Expected result:** Women will be deemed adherent to the interventions if  $\geq 80\%$  of the supplements provided are consumed.

**Health Status Monitoring.** Health status will be assessed weekly through text messaging via texting service SimpleTexting (subject will be contacted by phone if additional information is needed beyond what is captured by text) and at monthly research visits. SimpleTexting is a HIPPA compliant online texting service. Subjects will receive this message on their smartphone. The SimpleTexting account is password protected and only accessible by key research personnel. Reported health changes will be reviewed and coded using a standardized approach. This information will be stored in REDCap. Other maternal (e.g., preeclampsia, gestational diabetes mellitus, infections), pregnancy (e.g., spontaneous pre-term birth), fetal (e.g., amniotic fluid index measured clinically in the second and third trimesters) and neonatal (e.g., birth weight, hypoglycemia) health outcomes will be collected from the subject EMR. We anticipate the most frequently reported health changes will be gastrointestinal (GI) in nature (e.g., constipation, loose stools). Therefore, a GI symptoms survey will be administered at each monthly in-person research encounter. **Expected result:** We expect that the type and rate of health events will be similar between study arms.

The research participants will complete 7-9 study visits depending on their gestational age when they enter the study. T1 (Screening/Baseline) will occur at 15-24 weeks gestation (WG), T2 will occur at 19-24 WG, T3 will occur at 23-28 WG, T4 will occur at 27-32 WG, T5 will occur at 31-36WG, T6 will occur at 35-40 WG, T7 will occur at 39-41WG, T8 will occur at delivery, and T9 will occur 2-3 days after delivery or at 38-42 weeks postmenstrual age for infants born preterm.

*Participants will receive cash for each completed study visit. If they screen out at baseline due to their PHQ-8 score (if applicable), they will receive \$10 and be withdrawn. If they do not finish the study, they will be compensated only for the visits they have completed. Participants will receive \$50 at baseline, \$20 at each monthly visit, and \$29 at delivery. If a participant completes all parts of the study, they will receive a total of \$179-\$199 in cash depending on when they entered the study, compensation for UIC parking and/or public transportation costs, and a baby-related gift with a cash value of approximately \$101 (car seat, highchair or bassinet). Participants will receive another baby-related gift with a cash value of approximately \$101 (car seat, highchair or bassinet) if they agree and complete ABR testing. Participants will choose a gift from the gift catalog provided by a member of the research team. Participants who screen out for PHQ-8 (if applicable) will receive \$10 and compensation for UIC parking or public transportation costs.*

*We will monitor hemoglobin and iron status monthly at study visits and review results weekly with [name], the medical oversight physician for the study. If needed, [name] will coordinate care with the participant's primary practitioner.*

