## 1.0 Project Summary/Abstract

*Maternal iron deficiency anemia (IDA) increases the risk of adverse pregnancy outcomes and can negatively impact the iron endowment of the neonate that may cause irreversible deleterious effects on neurodevelopment. To avert IDA in pregnancy, women are universally prescribed a daily oral supplement containing ~27 mg of iron. However, there is growing concern regarding the efficacy of this one-size-fits-all approach for women with systemic inflammation, including women with obesity. Obese women experience disruption to the hepcidin-ferroportin complex deeming iron from diet, including supplemental iron, and body stores less bioavailable. This indicates an urgent need to develop and test new methods to prevent maternal IDA among women with obesity. In this planning grant application, we will develop the clinical and research infrastructure to test the preliminary efficacy of oral lactoferrin (Lf) supplementation for the prevention of maternal IDA among obese women. Lactoferrin is a natural compound found in secretions from mammals, including milk, and is an important regulator of body iron balance given its effects on inflammation and the hepcidin-ferroportin complex. Daily oral Lf has been shown to be superior to oral iron supplementation for treating IDA in pregnant women with inflammation but has not been studied for its ability to prevent IDA in pregnancy. The specific aims of this clinical trial planning grant include: 1) Conduct provider facing one-on-one interviews to inform and optimize a clinical research intervention into the clinical infrastructure at the Center for Women's Health at UIC and, 2) Pilot test a randomized controlled trial of oral Lf supplementation from early second trimester up through delivery among 40 pregnant women with obesity at risk of IDA. In this aim we seek to understand recruitment, adherence, and retention rates and intervention acceptability to determine feasibility and preliminary efficacy on maternal inflammation and maternal and neonatal iron and hematological-related markers. This study will provide first of its kind data, necessary and sufficient to inform and develop a large-scale efficacy trial of oral Lf as a safe and scalable natural compound for the prevention of IDA among obese women. Ultimately if successful, this project is an important first step toward improving prenatal care for obese women who represent more than a third of reproductive-age women in the United States.*

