*Maternal Dietary Intake. Dietary macro- and micro-nutrient intake will be assessed using the web-based Diet History Questionnaire III (DHQ-III) food frequency questionnaire (baseline only). The DHQ-III will be self-administered. Recent dietary intake/supplement use will be assessed at baseline, T3, and T5, via Nutrition Data System for Research interviewer-assisted 24-hour diet recall software. Mean total, food, and supplemental iron intake can be estimated from both dietary measures.*

*Maternal Anthropometrics & Gestational Weight Gain. Maternal height will be measured using a fixed stadiometer (baseline only) and weight at baseline, monthly, and at admittance for labor and delivery with a calibrated digital scale. BMI will be calculated as kg/m^2. Pre-pregnancy weight will be self-reported (confirmed by EMR, if available) and used to derive gestational weight gain using published methods. Rationale for determining gestational weight gain is the reported evidence that excessive gestational weight gain can negatively affect maternal and neonatal iron status and regulation.*

*Neonatal Cord Iron Status & Hematological Parameters. Neonatal cord iron status and hematologic parameters will be assessed from venous umbilical cord blood obtained bedside following delivery of the placenta. Even with delayed umbilical cord-clamping, we can successfully obtain 40-50 milliliters of umbilical venous cord blood. We will employ our effective 24/7 call schedule (including holidays) with two team members on call daily to cover LD collections. We have an 87% (40 of 46 women) success rate of collecting samples bedside at delivery as indicated in our preliminary studies section.*

*Expected results: Compared with control, we expect the neonates born to women in the oral Lf group will have superior cord markers of iron status, cord TBI and cord Hb at delivery.*

- *Cord Ferritin & Iron. Cord ferritin and iron will be measured in serum by immunoassay and spectrophotometry at a local commercial lab (Quest Diagnostics, Wood Dale, IL).*
- *Cord sTFR. Cord sTFR will be measured with an immunoassay (ELISA) (R&D Systems, Minneapolis, MN). Our lab's intra-assay coefficient of variation (CV) for this kit is 5.3%.*
- *Cord TBI. Cord TBI will be calculated from cord sTFR and serum ferritin using a published equation.*

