*Additional Surveys & Questionnaires. Subjects will complete surveys pertaining to socio-demographics, reproductive/mental health, physical activity and medication/supplement use. If the participant is interested in completing questionnaires remotely in advance of the subsequent monthly visits after the baseline visit, they will have the option to receive a link via REDCap to the GAD 7, PSS 10, and PPAQ questionnaires which should be completed 1-3 days before their research visit. We will also obtain data at follow-up and supplement refill visits pertaining to health or medication/supplement changes since the last research-related visit that we will verify with the EMR.*

*Satisfaction Survey. Subjects will complete the Treatment Satisfaction Questionnaire for Medication (TSQM) to determine satisfaction with the interventions. The TSQM will assess participants' satisfaction with the effects and ease of taking the intervention supplements. There are 14 items in the TSQM that cover four domains: effectiveness (3 items), side effects (5 items), convenience (3 items), and global satisfaction (3 items). Expected results: Subject satisfaction with the oral Lf intervention will be determined by achieving a mean score  $\geq 70$ .*

*Overall trial acceptability. Semi-structured interviews using questions adapted from DasMahaptra et al. and Pflugeisen et al. will address multiple domains of participation in the trial including satisfaction with study visits, study staff, reimbursement, and intentions for participation in the trial. The interviews will be conducted one day after delivery in the patient's hospital room. We have used this technique in our other studies with success. Responses will inform refinement and implementation procedures for the larger efficacy trial.*

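### The 80% pill-count rule cannot see non-study iron in the lactoferrin arm or non-study lactoferrin in the control arm, so it does not measure adherence to the iron-free regimen

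*Combined protocol and SAP*

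**What the plan says.** Section 6.0 (Study Design; Study Arms) compares once-daily Lf 250 mg plus a prenatal supplement without iron against a standard prenatal supplement with iron. Figure 4 lists 28 mg of iron per softgel for the control product.

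Under Optimizing Adherence in the same section, "Hand pill counts will be performed by UIC Investigational Drug Service", and the rule is "Women will be deemed adherent to the interventions if" at least 80% "of the supplements provided are consumed". Non-study products are not mentioned.

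Four other places bear on the point:

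- Section 1.0 says that "women are universally prescribed a daily oral supplement containing ~27 mg of iron". Sections 4.0 and 5.0 place recruitment after the new OB visit, and supplementation starts at 15–24 weeks.
- Section 6.0 (Study Arms) says "Women will not be blinded to their treatment assignment". It explains the once-daily 250 mg choice partly as "due to the common availability of Lf formulations in the U.S. commercial market".
- Section 8.0 collects the relevant data. Diet recalls covering supplement use take place at baseline, T3 and T5, and "Mean total, food, and supplemental iron intake can be estimated from both dietary measures". In addition, "We will also obtain data at follow-up and supplement refill visits pertaining to health or medication/supplement changes", to be verified with the medical record.
- Section 9.0 plans intent-to-treat and as-treated effects but does not define as-treated.

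**The concern.** One arm is defined partly by something women do not take. A count of returned study capsules and gummies shows whether study product was used, but not whether a second product was used beside it. The rule nevertheless claims to measure adherence to the interventions as a whole.

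Three uses of the pilot are affected:

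- **Feasibility.** Adherence is an Aim 2a quantity. A later efficacy trial needs to know whether women stay on a prenatal product without iron, and the planned figure does not answer that.
- **As-treated analysis.** The 80% flag is the only exposure rule in the plan. If it were used to form the as-treated classes, women taking Lf plus iron would be grouped with women taking Lf instead of iron. The rationale in Section 2.0 concerns Lf without additional oral iron.
- **Interpretation of hemoglobin.** Section 7.0 expects no significant decrease in women who adhere to the regimen. Hemoglobin among pill-count adherent women would be read as evidence on the iron-free regimen, although some of them may be taking iron.

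**Working it through.** **The plan's own figures.** The 80% cut-off is a chosen threshold with no derivation to reproduce. The sample-size arithmetic reproduces: 32 / (1 − 0.20) = 40. The point does not depend on it.

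**Inputs.** Control product: 28 mg iron per day (Figure 4). Lf capsule: 250 mg, with iron at 17.6 mg per 100 g (Section 6.0, Study Arms). A woman's own product: about 27 mg iron per day (Section 1.0). The Lf-arm prenatal product is described as without iron.

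**Planned contrast per woman.**
- Iron in the capsule: 17.6/100 × 0.250 = 0.044 mg/day.
- Iron contrast: 28 − 0.044 = 27.96 mg/day.
- Lf contrast: 250 mg/day.

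**Lf-arm woman who adds her own 27 mg product.**
- Iron contrast: 28 − (27 + 0.044) = 0.96 mg/day.
- Share lost: 27 / 27.96 = 97%.
- Lf contrast: unchanged at 250 mg/day.
- Pill-count status: adherent if at least 80% of study product is taken.

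**Control woman who buys one 250 mg Lf capsule per day.**
- Lf contrast: 250 − 250 = 0.
- Iron contrast: essentially unchanged at about 28 mg/day.
- Pill-count status: adherent on the same condition.

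**Group level.** Let f be the share of Lf-arm women taking their own 27 mg product. The documents do not give f, so a range is assumed. Study product is taken as fully consumed, controls are assumed to take no second iron product, and the 0.044 mg is ignored. The mean iron contrast is then 28 − 27f.

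| Assumed f | Mean iron contrast (mg/day) | Women, if 30 in the Lf arm (30f) | Women, if 20 in the Lf arm (20f) |
|---|---|---|---|
| 0.10 | 25.3 | 3 | 2 |
| 0.25 | 21.25 | 7.5 | 5 |
| 0.50 | 14.5 | 15 | 10 |

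Two arm sizes are shown because Section 6.0 states 3:1 allocation (30 and 10 of 40) but also a final 16 per arm, which fits 1:1 (20 and 20). The counts are upper bounds on women misclassified as following the iron-free regimen: they assume that every co-user also passes the 80% count and that nobody leaves, while the plan assumes 20% attrition.

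**Can the recorded data supply the rate?** Yes, if combined. Follow-up visits ask about changes, so a woman who simply continues her own product may report none. Recalls are made only at baseline, T3 and T5, and a 24-hour recall alone cannot establish regular use. Baseline use, the visit record and the recalls therefore have to be read together under a written rule.

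**The case against.** The strongest reply is that taking assigned product and taking other product are different things, and that measuring the first by pill count is legitimate. That stands, and it argues against folding both into one flag, which would hide which failure occurred. It does not rescue a rule that presents the pill count as adherence to the whole intervention.

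A second reply is that as-treated ordinarily means what women actually took, and nothing ties it to the 80% flag. Also true. The gap there is an undefined term.

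A third is that co-use is conjecture. Universal prescription does not prove that a woman owns or continues a product, both arms receive a replacement prenatal product, and the remark on commercial availability explains the dose choice rather than showing that controls buy Lf. The consent pages were not available for review, so no instruction about women's own supplements can be called missing. All of this limits what can be said about frequency.

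A fourth is that the consequence is modest: adherence is not among the listed criteria for deeming the study feasible, and efficacy is descriptive and unpowered (Sections 9.0 and 12.0). That is fair, and it bears on the weight of the point rather than its correctness.

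Three stronger readings are tempting and not supported:

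- **The contrast between arms is lost.** It is not. Each co-user loses one of two components.
- **The hemoglobin difference shrinks.** Multiplying the expected 0.5 g/dL by 1 − f (0.45 at 10%) requires that co-users contribute no effect at all. Added iron could instead raise Lf-arm hemoglobin and widen the difference, or do little, given Section 2.0's premise that oral iron has limited efficacy under inflammation.
- **The pilot can give no contamination rate.** It can. The plan simply does not commit to deriving and reporting one.

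**Conclusion.** The point holds in a limited form. The adherence rule cannot detect non-study iron in the Lf arm or non-study Lf in the control arm, and nothing elsewhere in the plan corrects this. A Lf-arm co-user is effectively on Lf plus iron versus iron, rather than Lf in place of iron. A control co-user removes the other component.

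The per-woman figures follow from the stated product contents and the protocol's approximate 27 mg. The group figures rest on assumed co-use rates and show scale only. No direction or size of bias in hemoglobin is established. What changes is the conclusion the pilot can draw: the planned adherence rate describes use of study product, not maintenance of an iron-free regimen.

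**What to change.** 1. **Section 6.0.** Keep the 80% pill count, described as adherence to study product.
2. **Separate feasibility outcome.** Report by arm, with a 95% CI, the proportion using non-study iron (Lf arm) or non-study Lf (control). Derive it from baseline supplement use, the visit supplement-change record verified with the medical record, and the T3 and T5 recalls. State what counts as use, and that a product reported at baseline is treated as continuing until a stop is recorded.
3. **Section 9.0.** Define the as-treated classes by actual iron and Lf exposure from these data, not by the pill-count flag alone.
4. **Iron prescribed after the hemoglobin review.** Show it separately, since it arises from clinical care rather than from products a woman already has or buys.

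The cost is protocol and SAP wording and a small derivation, with no new visits, samples or participants. Fewer women may be classed as having followed the iron-free regimen. What women are told about their own supplements is left to the clinical team.
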